8.4 Visit Windows

Visit windows will be defined for the purpose of classifying assessments to be used in the analysis in the case that an assessment is obtained outside scheduled assessment times or if multiple assessments are collected. If multiple valid nonmissing assessments exist in an analysis window, then the following rules will be used to choose the assessment for the analyses:

- The assessment on the date closest to the date of the nominal day of that visit will be selected.
- If there are 2 assessments with equal distance from the nominal day, the one on the latest date will be selected.
- If there is more than 1 assessment on the selected date, the average will be taken and used for the analyses.

8.4.1 Laboratory Parameters

For the laboratory (hematology, coagulation and chemistry) parameters, Table 1 below provides the analysis windows for the purpose of identifying the assessments to be used in the analyses during the prophylaxis phase. Table 2 provides the analysis windows for the rescue phase.

Table 1 - Analysis Window for Laboratory Parameters During Prophylaxis Phase

Visit Identifier	Nominal Day	Lower Limit: HSCTSTDY	Upper Limit: HSCTSTDY
Baseline		The last nonmissing value collected on or before the first dose.	
Day +1 post-HSCT	HSCTSTDY=2	1	4
Day +7 post-HSCT	HSCTSTDY=8	5	11
Day +14 post-HSCT	HSCTSTDY=15	12	18
Day +21 post-HSCT	HSCTSTDY=22	19	25
Day +30 post-HSCT	HSCTSTDY=31	26	34
Day +37 post-HSCT	HSCTSTDY=38	35	41
Day +44 post-HSCT	HSCTSTDY=45	42	48
Day +51 post-HSCT	HSCTSTDY=52	49	55
Day +60 post-HSCT	HSCTSTDY=61	56	66
Day +100 post-HSCT	HSCTSTDY=101	96	106
Day +180 post-HSCT	HSCTSTDY=181	171	191

HSCTSTDY = DATE – (Date of Day +0 post-HSCT) + 1, where DATE is the date of the lab assessment.

Table 2 - Analysis Window for Laboratory Parameters During Rescue Phase

Visit Identifier	Nominal Day	Lower Limit: HSCTSTDY	Upper Limit: HSCTSTDY
Baseline		The last nonmissing value collected on or before the first dose.	
Day +1 post-VOD Treatment	HSCTSTDY=2	1	4
Day +7 post-VOD Treatment	HSCTSTDY=8	5	11

Day +14 post-VOD Treatment	HSCTSTDY=15	12	18
Day +21 post-VOD Treatment	HSCTSTDY=22	19	25
Day +30 post-VOD Treatment	HSCTSTDY=31	26	34
Day +37 post-VOD Treatment	HSCTSTDY=38	35	41
Day +44 post-VOD Treatment	HSCTSTDY=45	42	48
Day +51 post-VOD Treatment	HSCTSTDY=52	49	55
Day +60 post-VOD Treatment	HSCTSTDY=61	56	64
Day +67 post-VOD Treatment	HSCTSTDY=68	65	71
Day +30 post-HSCT ^a	HSCTSTDY=31	26	34
Day +100 post-HSCT ^a	HSCTSTDY=101	96	106
Day +180 post-HSCT ^a	HSCTSTDY=181	171	191

HSCTSTDY = DATE – (Date of Day +0 post-VOD Treatment) + 1, where DATE is the date of the lab assessment.

^a HSCTSTDY = DATE – (Date of Day +0 post-HSCT) + 1, where DATE is the date of the lab assessment. If Day +30, +100 or +180 post-HSCT visit occurs during the Rescue Phase, the corresponding records will be summarized twice (once at post-VOD Treatment summary and once at post-HSCT summary).

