### 7.2.3 Day+30 Post-HSCT Visit

The daily efficacy assessments (including physical exam, weight, and total bilirubin; see [Section 7.2.1.2](#) and [Appendix 1](#)) performed on Day +30 post-HSCT support the evaluation of the primary efficacy endpoint for this study. Patients should have this assessment performed on Day +30 post-HSCT (-2 to 0 days) wherever possible. The following procedures will also be performed on Day +30 post-HSCT (-2 to 0 days) (if the twice weekly visit falls within the Day +30 post-HSCT window of -2 to 0 days, the Day +30 post HSCT assessments should be performed at that visit).

- Karnofsky PS ( $\geq 16$  years of age)
- Lansky PS ( $< 16$  years of age)
- EQ-5D-5L (adults)
- EQ-5D-Y (pediatric patients and parents [proxy version 1])
- Neutrophil and platelet engraftment/graft failure (see [Section 6.8.6](#))
- Abdominal ultrasound (to assess liver and ascites)
- Serum/urine pregnancy test, for females of childbearing potential only
- Acute GvHD
- Relapse of malignant disease
- Monitoring for VOD (i.e., total bilirubin, hepatomegaly, ascites, weight gain, biopsy [as applicable])
- Monitoring for VOD-associated MOD (i.e., serum creatinine/CrCl or GFR [optional]/dialysis and supplemental oxygen/ventilator support)
- \*PK sample (for patients still receiving defibrotide; see [Section 6.6.2.1](#) and [Section 6.6.2.2](#) for PK populations and exact time points)
- Immunogenicity sample (patients randomized to DP arm; see [Section 6.7.1](#))

\*Note: PK sampling can be eliminated if investigator believes such sampling will compromise patient safety ([Appendix 6](#)) with the reason for omitting samples clearly documented.

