### **7.3.2 Day +100 Post-Hematopoietic Stem Cell Transplant (-7 to 0 days) (DP and BSC Arms)**

The following procedures and assessments are to be performed or information will be collected at Day +100 post-HSCT (-7 to 0 days):

- Physical examination, including assessments of the skin, head, eyes, ears, nose, throat, neck, thyroid, lungs, heart, abdomen (with palpation of the liver; and with measurement of abdominal girth for pediatric patients only), lymph nodes, extremities, and a general assessment (including edema). Whenever possible, assessment of right upper quadrant pain will be performed.
- Weight
- Vital signs (blood pressure, pulse, respiratory rate, and body temperature)
- Karnofsky PS ( $\geq 16$  years of age)
- Lansky PS ( $< 16$  years of age)
- EQ-5D-5L (adults only)
- EQ-5D-Y (pediatric patients and parents [proxy version 1])
- Clinical laboratory tests (serum chemistry, hematology, and coagulation)
- Calculation of CrCl (using Cockcroft-Gault for adults and Schwartz formula for pediatric patients). If cystatin C is measured, GFR will be calculated using either the Grubb or Larsson formula.
- Neutrophil and platelet engraftment/graft failure (see [Section 6.8.6](#))
- Abdominal ultrasound (to assess liver and ascites)
- Acute GvHD (i.e., rash, total bilirubin, stool output)
- Chronic GvHD (i.e., rash, mouth, eyes, gastrointestinal tract, liver function tests, lungs, joints and fascia, genital tract, and other symptoms, as clinically indicated)
- Monitoring for VOD (i.e., total bilirubin, hepatomegaly, ascites, weight gain, biopsy [as applicable])
- Relapse of malignant disease
- Monitoring for VOD-associated MOD (i.e., serum creatinine/CrCl or GFR [optional]/dialysis and supplemental oxygen/ventilator support)
- Immunogenicity sample (patients randomized to DP arm; see [Section 6.7.1](#))
- Hospitalization information (i.e., dates of hospitalization, dates in ICU, dates of readmission) and inpatient resource use
- Monitoring of SAEs considered to be related to study drug

- Survival status

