### 7.3.3 Day +180 Post-Hematopoietic Stem Cell Transplant, Study Completion, or Early Termination (DP and BSC Arms)

The following procedures and assessments are to be performed or information will be collected at Day +180 post-HSCT, study completion, or early termination ( $\pm 30$  days):

- Physical examination, including assessments of the skin, head, eyes, ears, nose, throat, neck, thyroid, lungs, heart, abdomen (with palpation of the liver; and with measurement of abdominal girth for pediatric patients only), lymph nodes, extremities, and a general assessment (including edema). Whenever possible, assessment of right upper quadrant pain will be performed.
- Weight
- Vital signs (blood pressure, pulse, respiratory rate, and body temperature)
- Karnofsky PS ( $\geq 16$  years of age)
- Lansky PS ( $< 16$  years of age)
- EQ-5D-5L (adults only)
- EQ-5D-Y (pediatric patients and parents [proxy version 1])
- Clinical laboratory tests (serum chemistry, hematology, and coagulation)
- Calculation of CrCl (using Cockcroft-Gault for adults and Schwartz formula for pediatric patients). If cystatin C is measured, GFR will be calculated using either the Grubb or Larsson formula.
- Neutrophil and platelet engraftment/graft failure (see [Section 6.8.6](#))
- Abdominal ultrasound (to be performed only if the patient's total bilirubin is  $> 2.0$  mg/dL or the patient has signs/symptoms of VOD)
- Acute GvHD (i.e., rash, bilirubin, stool output)
- Chronic GvHD (i.e., rash, mouth, eyes, gastrointestinal tract, liver function tests, lungs, joints and fascia, genital tract, and other symptoms, as clinically indicated)
- Monitoring for VOD (i.e., total bilirubin, hepatomegaly, ascites, weight gain, biopsy [as applicable])
- Relapse of malignant disease
- Monitoring for VOD-associated MOD (i.e., serum creatinine/CrCl or GFR [optional]/dialysis and supplemental oxygen/ventilator support)
- Immunogenicity sample (patients randomized to DP arm; see [Section 6.7.1](#))
- Hospitalization information (i.e., dates of hospitalization, dates in ICU, dates of readmission) and inpatient resource use
- Monitoring of SAEs considered to be related to study drug
- Survival status

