8.4.2 Karnofsky and Lansky Performance Scores

For the Karnofsky and Lansky performance scores, Table 3 provides the analysis windows for the purpose of identifying the assessments to be used in the analyses.

Table 3 - Analysis Window for Karnofsky and Lansky Performance Scores

Visit Identifier	Nominal Day	Lower Limit: HSCTSTDY	Upper Limit: HSCTSTDY
Baseline		The last nonmissing value collected on or before the first dose.	
Day +0 post-VOD Treatment ^a	HSCTSTDY=1	1	4
Day +1 post-HSCT	HSCTSTDY=2	2	5
Day +7 post-HSCT	HSCTSTDY=8	6	12

Day +15 post-HSCT	HSCTSTDY=15	13	25
Day +30 post-HSCT	HSCTSTDY=31	26	51
Day +60 post-HSCT	HSCTSTDY=61	52	81
Day +100 post-HSCT	HSCTSTDY=101	82	141
Day +180 post-HSCT	HSCTSTDY=181	142	191

HSCTSTDY = DATE – (Date of Day +0 post-HSCT) + 1, where DATE is the date of the lab assessment.

^a Rescue Phase only. HSCTSTDY = DATE – (Date of Day +0 post-VOD Treatment) + 1, where DATE is the date of the lab assessment.

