8.4.3 Vital Signs

Intensive vital signs recorded during the first and second infusion of defibrotide on the first day of defibrotide dosing will be summarized at the nominal visit and time recorded in EDC. The analysis windows for all other visits will follow Table 1 and Table 2 in [Section 8.4.1](#) for the prophylaxis and rescue phases, respectively.

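### The SAP's Day +180 laboratory and vital-sign window covers only 21 of the 61 protocol-compliant dates, and its Day +100 window misses 2 of 8; the Day +180 performance-score window also stops short.

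*SAP*

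**What the plan says.** SAP 8.4.1 introduces its laboratory windows with the words "Table 1 below provides the analysis windows for the purpose of identifying the assessments to be used in the analyses during the prophylaxis phase". For the rescue phase, Table 2 does the same and repeats the Day +100 and Day +180 post-HSCT rows. The Day +180 row reads "Day +180 post-HSCT HSCTSTDY=181 171 191", and the Day +100 row has limits 96 and 106. For these rows HSCTSTDY is the assessment date minus the Day +0 date, plus 1.

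For vital signs other than the intensive monitoring around the first two infusions, SAP 8.4.3 says: "The analysis windows for all other visits will follow Table 1 and Table 2 in" the laboratory section. For performance scores, SAP 8.4.2 says "Table 3 provides the analysis windows for the purpose of identifying the assessments to be used in the analyses"; its Day +180 row runs from 142 to 191. SAP 11.3, 11.4 and 11.7 refer back to these sections for the values or visits to be summarised.

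Protocol 7.3.3 lists laboratory tests, vital signs and performance scores among the "information will be collected at Day +180 post-HSCT, study completion, or early termination", with a window of ±30 days. Protocol 7.3.2 sets the Day +100 visit at -7 to 0 days. Protocol 7.4.2.4, 7.4.2.5 and both schedule appendices give the same windows.

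**The concern.** An analysis window should take in at least every date on which the protocol permits the visit. If it does not, a site can follow the protocol exactly, collect the value, and still see it left out of the visit summary. In Table 1 nothing catches such a value: Days +66 to +94, +106 to +169, and +191 onward belong to no visit, and the SAP gives no fallback rule. At stake is how complete the Day +100 and Day +180 summaries are for laboratory values, vital signs and performance scores, including change from baseline and the by-visit vital-sign shift table.

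Protocol 9.14.2 and 9.14.3 tie the laboratory and vital-sign presentations to the protocol's visit schedule. SAP section 5, which records changes to the planned analyses, does not mention a tighter window.

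**Working it through.** **Conversion.** HSCTSTDY = X + 1 for Day +X. This reproduces every nominal day in Table 1: 180 + 1 = 181, 100 + 1 = 101, 60 + 1 = 61, 30 + 1 = 31. A limit of L therefore means Day +(L - 1).

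**Inputs.** SAP limits come from Tables 1 to 3. Protocol windows come from 7.3.1 (Day +60, ±3), 7.3.2 (Day +100, -7 to 0), 7.3.3 (Day +180, ±30) and 7.2.3, which says "Patients should have this assessment performed on Day +30 post-HSCT (-2 to 0 days) wherever possible".

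**Tables 1 and 2 (laboratory and vital signs; the Day +60 row is from Table 1).**

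| Visit | Protocol dates | SAP dates | Compliant dates missed |
|---|---|---|---|
| Day +30 | +28 to +30 (3) | +25 to +33 (9) | 0 |
| Day +60 | +57 to +63 (7) | +55 to +65 (11) | 0 |
| Day +100 | +93 to +100 (8) | +95 to +105 (11) | +93, +94: 2/8 = 25% |
| Day +180 | +150 to +210 (61) | +170 to +190 (21) | +150 to +169 and +191 to +210: 20 + 20 = 40; 40/61 = 65.6% |

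The weekly windows between Days +31 and +60 are contiguous in Table 1 and lose nothing. In Table 2 a missed date may still count in a post-VOD Treatment row, which runs up to 70 days after rescue starts, but it enters no post-HSCT row.

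**Table 3 (performance scores).** Day +180 is HSCTSTDY 142 to 191, which is Days +141 to +190. Compliant dates missed: +191 to +210, so 20/61 = 32.8%. Day +100 is 82 to 141, which is Days +81 to +140, and misses none.

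**Day +15 nominal value in Table 3.** By the formula, 15 + 1 = 16; the table prints 15, while its other post-HSCT rows follow X + 1. SAP 8.4 selects the value closest to the nominal day. With scores on HSCTSTDY 14 and 17, a nominal day of 15 picks the first (distance 1 against 2) and a nominal day of 16 picks the second (2 against 1). No value is excluded by this slip; it only affects which score is chosen.

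**From dates to patients at Day +180.** The documents give no distribution of visit dates, so only scenarios are possible:
- all visits within ±10 days: none lost;
- triangular around Day +180, with weight 31 - |k| at k days from nominal: total 31² = 961, excluded 2 × (1 + 2 + ... + 20) = 420, so 420/961 = 44% lost;
- even spread over the 61 dates: 66% lost.

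**The case against.** The best counter-argument lies in the opening of SAP 8.4, which says windows serve to classify assessments made outside scheduled times or more than once per visit. A single draw on a compliant date is neither, so it could be read as staying at its recorded visit. That reading is possible, and it makes the exclusion less certain. But 8.4.1, 8.4.3 and 11.3 use the windows to identify the values analysed, without that condition. The only measurements expressly kept at their recorded visit are the intensive vital signs. A programmer working from Tables 1 and 2 would most naturally drop the compliant values.

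The second argument is that little depends on it, and much of that stands. Adverse-event summaries do not use these windows. The laboratory shift table takes the highest grade after baseline, and the maximum blood-pressure change is not defined by visit. All laboratory results are listed. The primary and key secondary endpoints have their own date rules. No test is attached to the affected summaries, and both arms share the same windows. Prophylaxis ends by Day +30, so for patients not rescued Day +180 is about five months later.

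A reader might infer that the SAP windows are narrower than the protocol's throughout. They are not: Days +30 and +60 are wider, and Day +100 is wider but shifted. Of the windows in Tables 1 and 2 compared above, only Day +180 is narrower.

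**Conclusion.** The mismatch is real and worth correcting, and its reach is limited. As written, 40 of 61 compliant Day +180 dates (66%) and 2 of 8 compliant Day +100 dates (25%) fall in no post-HSCT laboratory or vital-sign window. For performance scores, 20 of 61 Day +180 dates (33%) are missed. The date counts need no assumption beyond the formula in the tables. That the values are left out rests on the plain reading of 8.4.1 and 8.4.3.

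A reader might infer that two thirds of patients lose their Day +180 values. The documents do not support that: 66% is a share of calendar dates and becomes a share of patients only under an even spread of visits. The true figure could be zero. Nor do they support saying that the late safety profile as a whole, or any efficacy result, rests on a selected subset. What is affected is the set of by-visit descriptive summaries named above.

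**What to change.** - In Tables 1 and 2, set the Day +180 post-HSCT window to HSCTSTDY 151-211 (Days +150 to +210) and the Day +100 post-HSCT window to 94-106 (Days +93 to +105). Neither overlaps another post-HSCT row. Vital signs follow automatically through 8.4.3.
- In Table 3, raise the Day +180 upper limit from 191 to 211 and keep the lower limit at 142. The Day +100 row ends at 141, so moving the lower limit to 151 would leave HSCTSTDY 142-150 in no window.
- In Table 3, change the Day +15 nominal value from 15 to 16.
- It would also help to state in 8.4 whether a protocol-compliant visit keeps its recorded visit label.

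With these limits no compliant date at Day +100 or Day +180 is excluded. The cost is an edit to three SAP tables and the matching programming, best made before the database freeze that SAP section 3 sets as the deadline for analysis decisions. No new data are needed.

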4.2.2 Secondary Objectives

The key secondary objective of the study is to compare the efficacy of defibrotide prophylaxis in addition to BSC (DP arm) vs BSC alone (BSC arm) for the prevention of VOD as measured by VOD-free survival by Day +100 post-HSCT in subjects who are at high risk or very high risk for developing VOD.

Other secondary objectives of the study are as follows:

- To further compare the efficacy of defibrotide prophylaxis in addition to BSC (DP arm) vs BSC alone (BSC arm) on additional variables as follows:
 - Incidence of VOD by Day +30 post-HSCT
 - VOD-free survival by Day +180 post -HSCT
 - Non-relapse mortality (NRM) by Days +100 and +180 post-HSCT
 - Incidence of VOD-associated multi-organ dysfunction (MOD) (ie, severe VOD) by Days +30 and +100 post-HSCT (in those subjects who develop VOD)
 - Resolution of VOD by Day +180 post-HSCT and time to resolution of VOD (in those subjects who develop VOD)
 - Incidence of VOD after Day +30 post-HSCT up to Days +100 and +180 post-HSCT
- To compare the health-related quality of life using the following questionnaires:
 - 5-Level EuroQol-5D (EQ-5D-5L) (adults only)
 - EuroQol-5D for Youth (EQ-5D-Y), proxy version 1 (pediatric subjects 4 to 7 years of age)
 - EQ-5D-Y, self-report version 1 (pediatric subjects 8 to <16 years of age)
- To characterize the pharmacokinetics of defibrotide
- To compare the overall safety of defibrotide in addition to BSC vs BSC alone, including adverse event (AE) profile, serious adverse event (SAE) profile, laboratory abnormalities, and vital signs (including peri-infusional vital signs for subjects who receive defibrotide)
- To compare the overall safety of defibrotide in addition to BSC vs BSC alone by comparing the incidence of Grades 2, 3, and 4 acute GvHD by Days +30, +100, and +180 post-HSCT, and the incidence of chronic GvHD by Day +180 post-HSCT
- To compare graft failure and time to neutrophil and platelet engraftment

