8.2.3 Day +0 Post-HSCT

Day +0 post-HSCT is defined as the 0th day after HSCT; that is, the day of HSCT. For subjects in the ITT Analysis Set who do not have HSCT, Day +0 post-HSCT is the 0th day after randomization; that is, the day of randomization. For the analyses of all efficacy endpoints, duration calculations will start at Day +0 post-HSCT.

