8.3 Study Phase

In this study, the occurrence of VOD and the administration of rescue defibrotide represent a clinical landmark time point for safety. Therefore, for the safety analyses, 2 study phases are defined with respect to the administration of rescue defibrotide, as follows:

- **Prophylaxis Phase:**
 - If VOD occurs, the prophylaxis phase starts on the Baseline date and ends on the day before the start date of rescue defibrotide (ie, rescue treatment start date – 1).
 - If VOD does not occur, the prophylaxis phase starts on the Baseline date and ends on the date of study completion/early termination.
- **Rescue Treatment Phase:**
 - For the subset of subjects who developed VOD and received rescue defibrotide, the rescue treatment phase begins on the start date of rescue defibrotide and ends on the date of study completion/early termination.

The start date of rescue defibrotide will be derived as the date of the first administration of defibrotide on or after the investigator diagnosis of VOD.

Unless otherwise noted, safety summaries will be reported by study phase and by treatment received during the Prophylaxis Phase.

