11.3 Laboratory Assessments

For all hematology, coagulation, and chemistry parameters, the lab values at baseline and each of the postbaseline assessments will be summarized and presented using descriptive statistics. See Section [8.4.1](#) for the identification of the assessments used in the analyses. For each of the postbaseline assessments, change between baseline and that assessment in a specific lab value will be calculated as follows,

Change from baseline = [Lab value at the post-baseline assessment] – [Lab value at baseline],

and will be summarized and presented using descriptive statistics. If the lab value is missing at either baseline or a specific post-baseline assessment for a subject, change from baseline will be missing.

- Summary of clinical laboratory results: Hematology
- Summary of clinical laboratory results: Chemistry
- Summary of clinical laboratory results: Coagulation

For each of the following select laboratory parameters: total bilirubin, serum creatinine, absolute neutrophil count, and platelet count, a shift table from baseline grade to the highest postbaseline grade will be provided:

- Shift table of selected postbaseline laboratory results from baseline

All laboratory results will be listed. In addition, a listing of subjects who have abnormal postbaseline lab values for select lab parameters (total bilirubin, serum creatinine, absolute neutrophil count, and platelet count) will be provided with corresponding normal ranges. The following listings will be provided:

- Listing of clinical laboratory results: Hematology
- Listing of clinical laboratory results: Chemistry
- Listing of clinical laboratory results: Coagulation

- Listing of subjects with abnormal post-baseline laboratory values

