11.4 Vital Signs

Systolic blood pressure, diastolic blood pressure, pulse rate, respiratory rate, and body temperature at baseline and each of the post-baseline assessments will be summarized and presented using descriptive statistics. See Section 8.4.3 for the identification of the assessments used in the analyses. For each of the post-baseline assessments, change between baseline and that assessment in a specific vital sign will be calculated as follows,

$$\text{Change from baseline} = [\text{Vital sign at the post-baseline assessment}] - [\text{Vital sign at baseline}],$$

and will be summarized and presented using descriptive statistics. If a specific type of vital signs is missing at either baseline or a specific post-baseline assessment for a subject, change from baseline will be missing.

Maximum decrease and increase from baseline in systolic and diastolic blood pressure will be summarized separately using descriptive statistics, to assess the potential for defibrotide to cause peri-infusional hypotension.

Baseline and post-baseline values for each visit in Section 8.4.3 will be categorized as low, normal, or high and presented on a shift table based on the criteria listed in Table 4.

Table 4 – Vital Signs Normal Ranges

Parameter	Low	Normal	High
Systolic blood pressure	< 60 mmHg	≥60 and ≤160 mmHg	>160 mmHg
Diastolic blood pressure	<50 mmHg	≥50 and ≤100 mmHg	>100 mmHg
Pulse rate	<40 beats per min.	≥40 and ≤120 beats per min.	>120 beats per min.
Respiratory rate	<10 breaths per min.	≥10 and ≤40 breaths per min.	>40 breaths per min.
Temperature	<36 degrees Centigrade	≥36 and ≤39 degrees Centigrade	>39 degrees Centigrade

The following summaries will be provided:

- Summary of vital signs
- Summary of maximum decrease and increase from baseline in systolic and diastolic blood pressure
- Shift table of vital signs results from baseline

The following listings will be provided:

- Listing of vital signs

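### SAP Table 1 has no laboratory or routine vital-sign window between first dose and transplant, and the worst-grade laboratory shift covers only four tests: a minor gap in descriptive safety tables

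*SAP*

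**What the plan says.** - **Windows.** SAP 8.4.1 introduces its first table thus: "Table 1 below provides the analysis windows for the purpose of identifying the assessments to be used in the analyses during the prophylaxis phase". The Baseline row takes the last non-missing value on or before the first dose. The next row, Day +1 post-HSCT, runs from HSCTSTDY 1 to 4. HSCTSTDY is the assessment date minus the transplant date plus 1, so HSCTSTDY 1 is the day of transplant.
- **Vital signs.** Apart from the intensive readings at the first two infusions, SAP 8.4.3 says: "The analysis windows for all other visits will follow Table 1 and Table 2".
- **Phase.** Under SAP 8.3, "the prophylaxis phase starts on the Baseline date". Conditioning therefore lies inside it.
- **Choice within a window.** SAP 8.4: "The assessment on the date closest to the date of the nominal day of that visit will be selected".
- **Patients without transplant.** SAP 8.2.3: "For subjects in the ITT Analysis Set who do not have HSCT, Day +0 post-HSCT is the 0th day after randomization".
- **Outputs.** SAP 11.3 refers to 8.4.1 for the assessments used in the by-visit laboratory summaries. It then adds: "For each of the following select laboratory parameters: total bilirubin, serum creatinine, absolute neutrophil count, and platelet count, a shift table", from baseline to the highest post-baseline grade. SAP 11.4 says: "Baseline and post-baseline values for each visit in Section 8.4.3 will be categorized as low, normal, or high and presented on a shift table". It also summarizes the maximum change in blood pressure.
- **Objective.** SAP 4.2.2 includes among the safety comparisons "serious adverse event (SAE) profile, laboratory abnormalities, and vital signs".
- **Protocol.** Section 7.2.1.2 collects laboratory tests and vital signs daily in hospital from Study Day 2. Section 9.14.2 plans the number and percentage of patients with abnormal post-baseline values for each laboratory parameter.

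**The concern.** The days between first dose and transplant are on-drug days in the DP arm: prophylaxis is started before conditioning by design. The protocol collects numeric laboratory and vital-sign data on those days, and the SAP places them in the Prophylaxis Phase, yet its windowing rule gives them no row. A change in a laboratory value or routine vital sign that is confined to conditioning, and that the investigator does not report as an adverse event, has no by-visit comparison between the arms. The trial is open-label, and adverse-event reporting of a laboratory change depends on a judgement of clinical significance. Numeric values do not.

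A second shortfall is independent of the windows. The protocol plans abnormal counts for each laboratory parameter; the SAP supplies a worst-grade shift, and a listing of abnormal values, for total bilirubin, creatinine, neutrophils and platelets only. SAP Section 5, which records departures from the protocol, does not mention the reduction. Hemorrhage is a named risk of defibrotide (protocol 1.6.1), but hemoglobin, INR and aPTT, like AST and ALT, are summarized only in the windowed by-visit tables.

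**Working it through.** **Inputs.** Conditioning lasts 5 days (the assumption in protocol 1.3). Study Day 1 is the day before conditioning in DP and the first day of conditioning in BSC (protocol 7.2). I take transplant (Day 0) as the day after conditioning ends. HSCTSTDY = date - Day 0 + 1.

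**1. Check against the protocol's own timeline.** Conditioning runs from Day -5 to Day -1, so DP Study Day 1 is Day -6. Study Day 21 is then -6 + 20 = Day +14. Protocol 1.3 says approximately Day +15. The calendar agrees to within a day.

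**2. Map the days to Table 1.**

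| Arm | Study Days | Relative to transplant | HSCTSTDY | Table 1 row |
|---|---|---|---|---|
| DP | 2-6 | Day -5 to -1 | -4 to 0 | none |
| DP | 7-10 | Day 0 to +3 | 1 to 4 | Day +1 |
| BSC | 2-5 | Day -4 to -1 | -3 to 0 | none |
| BSC | 6-9 | Day 0 to +3 | 1 to 4 | Day +1 |

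The lowest limit among the 11 post-baseline rows is HSCTSTDY 1. That leaves 5 days without a row in DP and 4 in BSC. The 5 DP days are 5/21 = 24% of the recommended minimum dosing period.

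**3. Range.** With conditioning of c days, the gap is c days in DP and c - 1 in BSC. For c = 4 to 8 (my assumption) it is 4 to 8 days in DP and 3 to 7 in BSC.

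**4. Values affected.** On the daily schedule a DP patient has 5 values per test in the gap. Bilirubin stays daily in hospital. At the permitted minimum frequency for other tests, evenly spaced (assumption), the expected number is:

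- hematology and other chemistry, three times weekly: 3/7 x 5 = 2.1 in DP and 3/7 x 4 = 1.7 in BSC;
- aPTT and INR, once weekly: 1/7 x 5 = 0.7 in DP and 1/7 x 4 = 0.6 in BSC.

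These are floors. The reduced schedule is meant for patients near the blood-draw limits (protocol Section 7).

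**5. Patients without transplant.** Their Day +0 is randomization, which falls on or before the baseline visit (protocol 7.1.2). Any value taken during conditioning therefore has HSCTSTDY of at least 1 and can land in a row labelled post-HSCT. The protocol expects fewer than 2% of patients in this position (9.8.1), that is fewer than 0.02 x 400 = 8.

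**6. What one added row can do.** SAP 8.4 keeps one date per window. A row with nominal day HSCTSTDY 0 takes the Day -1 value when testing is daily. The existing Day +1 row has nominal day HSCTSTDY 2, two days later. A change on DP Study Days 2-5 that resolves by Day -1 would still be in no by-visit row. Only a whole-phase worst-value summary counts it.

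**The case against.** The strongest reply is that little is lost. Treatment-emergent events count from the first dose of DP or conditioning (SAP 11.2), and clinically significant laboratory changes are recorded as adverse events (protocol 6.8.2.1). The pulmonary and gastrointestinal bleeding tables (SAP 11.2.1) include these days. First-day intensive vital signs are summarized, and every value is listed. The worst-grade shift and the maximum blood-pressure change state no window limit, so on a plain reading they already include conditioning. Keeping one value per window is the SAP's general design, so most daily values after transplant are left out too, and the protocol names no specific visit between baseline and Day +1. The Day +1, +7 and +14 rows still compare the arms while DP patients are on drug.

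Nearly all of that stands, and it sets the size of the point. Two things survive. First, every later stretch of daily inpatient collection has at least one row, and this one has none. Second, the four-test shift does not deliver what protocol 9.14.2 states. Moreover, SAP 11.3 points to the 8.4.1 windows before it describes the shift table, so a programmer could restrict that table to windowed values unless told otherwise.

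A reader might infer that safety data from conditioning go unanalyzed, or that early bleeding could be hidden. The documents do not support that, because the adverse-event and bleeding tables start at the first dose. Nor is the short list of shift tests a result of the windows; it is a separate choice in SAP 11.3.

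**Conclusion.** The gap is real and minor. Under 5-day conditioning, DP Study Days 2-6 and BSC Study Days 2-5 enter no by-visit laboratory or vital-sign summary and no per-visit vital-sign shift table, although they belong to the Prophylaxis Phase and bear on a stated secondary objective. The exact days depend on the length of conditioning; the absence of a row does not. Separately, SAP 11.3 falls short of protocol 9.14.2 on abnormal laboratory counts.

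The consequence is limited to descriptive safety output. No efficacy estimate, test or stopping rule is touched, and nothing here shows that a safety conclusion would change.

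**What to change.** 1. **Add one row to SAP Table 1**, labelled 'Conditioning (pre-HSCT)', from after the first dose through HSCTSTDY 0, with nominal day HSCTSTDY 0. Summarize it by arm for laboratory tests and routine vital signs. For patients who receive conditioning but no transplant, assign conditioning values to this row by their conditioning dates, not to post-HSCT rows counted from randomization.
2. **Extend the whole-phase worst post-baseline summary in SAP 11.3** to the other laboratory parameters, as protocol 9.14.2 states. At the least add hemoglobin, INR, aPTT, AST and ALT, which takes the tests from 4 to 9. Those five are a minimum and do not by themselves meet 9.14.2; if the SAP stops there, Section 5 should record the departure.
3. **State the data used.** Specify that this summary and the maximum blood-pressure change in SAP 11.4 use all values after the first dose, conditioning included. Transient changes that the single-value row misses are then counted.

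The cost is a few more table rows from data already collected. The aPTT and INR entries in the conditioning row will be sparse for patients on the reduced schedule, and with sparse testing the selected value may come from a day or more before Day -1. SAP Section 3 calls for analysis decisions before database freeze, so the change belongs in the SAP before then.
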